1.0 Objectives

Primary Objective

- 1.1 To estimate local control rates with image guided radiation therapy as defined in this study for patients with primary musculoskeletal tumors (MST).
 - 1.1.1 Prospectively establish a baseline estimate of local control for patients with MST (Ewing's sarcoma family of tumors (ESFT), rhabdomyosarcoma (RMS) and non-rhabdomyosarcoma soft tissue sarcoma (STS)) treated with image guided radiation therapy.
 - 1.1.2 Demonstrate that the increased level of conformality afforded by image guided radiation therapy does not reduce its efficacy relative to previously utilized non-image guided radiation therapy techniques in patients with Ewing's sarcoma family of tumors, resected soft tissue sarcomas, and group III rhabdomyosarcomas.
 - 1.1.3 Assess local and regional patterns of failure for patients with MST treated with image guided radiation therapy relative to their targeted volumes.
 - 1.1.4 Provide a long term (>5 year) estimate of local disease control for patients with MST (Ewing's sarcoma family of tumors (ESFT), rhabdomyosarcoma (RMS) and non-rhabdomyosarcoma soft tissue sarcoma (STS) treated with image guided radiation therapy.

Secondary Objectives

- 1.2 Establish a quantitative baseline estimate of radiation dose-related changes in normal tissues using novel objective measures of somatic change, musculoskeletal function, tissue biochemistry and physiology.
 - 1.2.1 Investigate the dose and volume relationship for the developing physis and cortical bone using physical measures and imaging evaluations including:
 - 1.2.1.1 Prospectively investigate whether an age based radiotherapeutic threshold of dose and volume that will induce premature physis closure and alter long bone length can be quantitatively identified.
 - 1.2.1.2 Quantitatively explore the impact of radiation on cortical bone thinning and long bone curvature.
 - 1.2.1.3 Relate radiation dose and volume to late (10+ year) alterations in bone integrity
 - 1.2.2 Describe the severity and time course of radiation-induced changes in the soft tissues and adjacent organs, including muscle and subcutaneous tissues.
 - 1.2.2.1 Delineate sequential changes in muscular volume, muscle function and organ function (delineated by imaging and measures of physical function) following image guided radiation for specific muscular groups.
 - 1.2.2.2 Correlate the temporal changes in muscular volume and function with changes in vascularity and metabolism defined by imaging studies.

Exploratory Objectives

1.3 Correlate changes in quantitative scales assessing quality of life (QOL) and function with range of motion and dosimetric parameters.

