2.1 Issues in the Radiotherapeutic Management of Pediatric Sarcomas

The delivery of radiotherapy to pediatric patients with sarcomas is complicated, as one must balance the appropriate dose and volume of treatment needed for local control with radiotherapy's potential effects on developing tissues. These goals are often at odds with one another as critical structures are closely related geometrically to targets, and radiation tolerances of structures are not fully defined; as radiation techniques advance toward greater conformity of the high dose region to the target, lower heterogeneous doses are distributed more broadly in adjacent tissues (1,2).

The local control rates for Ewing's family sarcoma, rhabdomyosarcoma, and nonrhabdomyosarcoma soft tissue sarcoma are defined using conventional radiation therapy techniques prior to the conformal radiation therapy era (3-10). These techniques often deliver relatively high radiation doses to normal tissue not considered at risk for harboring microscopic or gross tumor. Image guided techniques may allow sparing of these normal tissues. Brachytherapy has also been utilized as a form of adjuvant radiotherapy in these tumor types, most commonly for non-rhabdomyosarcoma soft tissue sarcoma (11). Retrospective reviews of brachytherapy in pediatric patients appear to result in favorable local control rates but prospective data to confirm the benefit of this modality is needed (12). The addition of imaging with CT scans to assist in targeting and planning of brachytherapy cases should enhance the delivery of this local modality. We will test the hypothesis that treatment of pediatric sarcomas with image guided radiotherapy techniques will maintain at least the current levels of local tumor control achieved with conventional techniques, while studying the impact of 3dimensional, image-guided radiation techniques to potentially decrease radiationrelated normal tissue effects.

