2.5.1 Primary Objectives

Patients with MST will have their target volumes (GTV, CTV and PTV) defined on planning imaging studies with anatomic and geometric margins defined in section 6.3. Target definitions are consistent with active national protocol guidelines when available. Radiation doses are prescribed relative to the PTV and are also consistent with available national protocol guidelines. Local tumor control will be evaluated by clinical exam and imaging studies as defined in section 10.1. Local control rates with image guided radiation therapy will be compared with expected rates of control using traditional techniques for patients with Ewing's sarcoma, resected soft tissue sarcoma and clinical group III rhabdomyosarcoma. Patients with rhabdomyosarcoma and nonrhabdomyosarcoma soft tissue sarcoma will have further reductions (by 5mm) in their clinical target volume (CTV) margins to remain consistent with national protocols. This group of patients will be monitored separately as well as together with the prior group of patients with RMS and STS for rates of local failure. This plan is outlined in statistical section 12.1. Local control and local/regional patterns of failure will be determined relative to the GTV, CTV, PTV, the volume irradiated to the prescription dose as noted in section 10.6 and primary site imaging parameters. The center or apparent origin of the recurrence will be considered when assigning a pattern of failure (appendix A).

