12.0 Statistical Considerations

12.1 To estimate the rates of local failure and tumor progression

The primary objective is to estimate the local control and patterns of failure for patients with primary musculoskeletal tumors including the Ewing's sarcoma family of tumors (ESFT), rhabdomyosarcoma (RMS) and non-rhabdomyosarcoma soft tissue sarcoma (STS) treated with image guided three-dimensional conformal radiation therapy. Different tumor types are accessioned to this study and their local failure rates differ significantly. To account for these differences, three groups of patients will be selected for local failure analysis based on the expected accrual of these patients to this study (Appendix E). These groups are defined by histology, site and degree of surgical resection and are selected to allow meaningful comparison with targeted rates of local control. Target local control rates for these specific treatment groups are established and listed in appendix E based on selected literature (3, 5-6, 9-12, 64,65). A lower limit to the local control rate is given to define a threshold below which the paradigm for treatment described in this protocol is deemed unacceptable. Analysis of local control will be undertaken for a treatment group at each event

Rev 5.2, dated: 6/9/2023 Protocol document date: 6/9/2023

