counted as a local failure, when each treatment group has completed accrual and has been followed for five years, and at intervals specified below. The accrual of patients in five years in the study for all tumor types is projected in Table 12.1.1 below. For the local control analysis, projections for accrual for the specific treatment groups are listed in Table 12.1.2 below. For nonsequential tests, if the actual final accruals are different from the projected accruals, then for Group III RMS or for the Resected or Small ESFT (target 85%), the lower limit to the local control rate is 60%, 70%, 72%, or 73.3%, respectively, for the final accrual of 15, 20, 25, or 30 patients. For the Resected STS (target rate 90%), the lower limit 73.3%, 75%, 76%, or 80%, respectively, for the final accrual of 15, 20, 25, or 30 patients. For the Large ESFT (target rate 55%), the lower limit 33.3%, 35%, 36%, or 40%, respectively, for the final accrual of 15, 20, 25, or 30 patients. A sequential safety-monitoring plan is given in Table 12.1.3 in terms of minimum number for the number of patients locally controlled corresponding to the number of patients accrued within a treatment group during the study, assuming the final accrual is 30 patients in each treatment group. The minimum number is calculated for each of the four treatment groups (Group III RMS, Resected STS, and Resected / Small ESFT, and Large ESFT), respectively. For each of the four treatment groups, when the number of patients accrued during the study reaches 5, 10, 15, 20, 25, or 30, the number of patients with local tumor control will be reviewed and must not be less than the corresponding minimum number (Table 12.1.3). If fewer patients than targeted are controlled locally, then the rate of local control is considered be too low for that treatment group and the study for that treatment group will be stopped for investigating the reasons. At any event counted as a local failure during study, the local control rate for that treatment group will be determined. If the local control rate is lower than targeted, then accrual to that treatment group will be halted and the reasons investigated. If the number of patients accrued is other than 5, 10, 20, 25, or 30, the assistance of the statistician ([name].) may be requested by the PI ([name]) to calculate the new minimum number of patients locally controlled according to the actual number of patients accrued. In the above monitoring scheme, the number of patients locally controlled is counted disregarding the timing (since initiation of radiation therapy) of events (local failures) as this calculation is based on a target rate of local control at 2 years that is identical at 5 years. These target rates are expected estimates of local control and not actual local control rates based directly on historic data. We will use the survival model with competing risk (e.g., patient death) (57) to estimate the rates of local failure and tumor progression (defined in 10.1-10.6) for each tumor group. One-hundred evaluable patients will be required based on the projected accruals in table 12.1.1 below. We expect to enroll a total of 110 patients based on our current accrual to generate 100 evaluable patients for analysis.

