Appendix D

Local control will be estimated for the patient groups indicated below.

Tumor groups are defined as follows:

Rhabdomyosarcoma (RMS)

Group III patients (biopsy or partial resection) followed by definitive radiation

Soft Tissue Sarcoma (STS)

Surgery consisting of a wide local excision (negative or positive margins) followed by radiation

Small or Resected Ewing's Sarcoma Family of Tumors (ESFT)

Surgery consisting of a wide local excision (negative or positive margins) followed by radiation for any primary site of disease

or

Definitive radiation therapy for any small primary site of disease (<8cm in greatest dimension at diagnosis)

Large Ewing's Sarcoma Family of Tumors (ESFT)

Definitive radiation therapy for any large primary site of disease (≥8cm in greatest dimension at diagnosis)

Defined 5 Year Local Control Rates for Evaluable Patient Groups Amend 2.0

	Group III RMS	Resected STS	Resected ESFT or Small ESFT	Large ESFT
Target Local Control Rate	85%	90%	85%	55%
Lower Limit LC Rate	71.4%	75%	66.7%	35%
Projected accrual (n)	28	24	18	12

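### Objective 1.1.2 sets out to demonstrate no loss of local control, but the only final criterion is not falling below a lower-tail limit, which cannot establish it

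*Combined protocol and SAP*

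**What the plan says.** Objective 1.1.2, a primary sub-objective, is to demonstrate that the added conformality "does not reduce its efficacy relative to previously utilized non-image guided radiation therapy techniques" in Ewing's tumors, resected soft tissue sarcoma and group III rhabdomyosarcoma. Section 2.1 states the hypothesis that the technique "will maintain at least the current levels of local tumor control achieved with conventional techniques". Section 2.5.1 adds: "Local control rates with image guided radiation therapy will be compared with expected rates of control using traditional techniques".

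Section 12.1 gives each group a target rate and a lower limit, the latter described as a "threshold below which the paradigm for treatment described in this protocol is deemed unacceptable". For the 85% target, "the lower limit to the local control rate is 60%, 70%, 72%, or 73.3%, respectively", for final accruals of 15, 20, 25 and 30. The second-phase paragraph calls the corresponding limits at n=35 and n=65 5% lower limits: 26 and 50 patients (85% target), 28 and 54 (90% target). Appendix D repeats targets and limits at first-phase accruals under the title "Defined 5 Year Local Control Rates for Evaluable Patient Groups".

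Section 12.1 also has sequential minimum counts every five patients (Tables 12.1.3 and 12.1.5) and a review at each local failure. It says that the targets are expected values and are not taken directly from historical data.

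**The concern.** Showing that efficacy is not reduced requires data that exclude a loss of some stated size. A limit set in the lower tail of the target's own distribution works the other way round: no loss is the starting assumption, and a group fails only if the data contradict it. Passing is then compatible with a material loss, and the fewer the patients, the lower the bar. Section 2.1 intends this cohort as a benchmark for later trials, so a conclusion of maintained control drawn from such a pass would carry forward without support.

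**Working it through.** **Inputs.** Targets 85% (Group III RMS; small/resected ESFT), 90% (resected STS) and 55% (Large ESFT). Printed limits from 12.1 and Appendix D. First-phase sizes 28, 24, 18 and 12 (Table 12.1.2, Appendix D). Second-phase sizes 35, 35, 13 and 12 (Table 12.1.4). Section 12.1 takes the two ESFT phases together for monitoring, giving 18+13=31 and 12+12=24.

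**1. Reproducing the printed limits.** With X binomial(n, target), take the smallest c for which P(X ≤ c) ≥ 0.05.

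- n=35, 85%: P(X≤25)=0.029, P(X≤26)=0.069, so c=26.
- n=65, 85%: P(X≤49)=0.028, P(X≤50)=0.055, so c=50.
- n=35, 90%: P(X≤27)=0.020, P(X≤28)=0.055, so c=28.
- n=65, 90%: P(X≤53)=0.026, P(X≤54)=0.057, so c=54.

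All four second-phase limits are matched. The limit is therefore a test of the null hypothesis that the rate equals the target.

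**2. Dependence on n (85% target).** 50/65=76.9%, 26/35=74.3%, 22/30=73.3%, 9/15=60%. A result exactly at the limit passes, yet its exact one-sided 95% lower bound is 67%, 59%, 57% and 36% respectively.

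**3. Chance that a real loss passes the final limit**, P(X ≥ limit | true rate), before any sequential look:

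| Group | n | Limit | 10-point loss | 15-point loss |
|---|---|---|---|---|
| RMS, second phase | 35 | 26 | 63% | 36.5% |
| STS, second phase | 35 | 28 | 60% | 32% |
| Small/resected ESFT | 31 | 23 (quantile, not printed) | 63% | 39% |
| Large ESFT | 24 | 9 (quantile, not printed) | 83% | 67% |
| 85% target, both phases | 65 | 50 | 42% | 14% |
| 90% target, both phases | 65 | 54 | 33% | 8% |

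At first-phase Appendix D sizes, a 15-point loss passes with probability 53% (RMS, P(X≥20 of 28 at 70%)), 61% (STS, P(X≥18 of 24 at 75%)) and 72% (small/resected ESFT, P(X≥12 of 18 at 70%)). The n=65 limit is also printed for small/resected ESFT, but that group's projected total is 31.

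**4. Adding the sequential looks.** The text of 12.1 acts when the count is below the minimum; the footnotes to Tables 12.1.3 and 12.1.5 act when it is at or below. Probability of clearing the looks and the final limit, text reading then footnote reading:

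- 10-point loss, second phase alone, n=35: RMS 62% or 57%; STS 59% or 54%.
- 10-point loss, both phases (30+35), all looks: RMS 32% or 19%; STS 27% or 19%.
- 15-point loss, first-phase sizes: n=28, 42% or 25%; n=24, 50% or 29%; n=18, 55% or 30%.

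**5. Consistency of the printed limits (minor).** On the step 1 convention, 9/15, 12/18 and 20/28 (85%), 15/20, 18/24 and 19/25 (90%) and 9/25 (55%) are each one patient low. They equal instead the largest c with P(X≤c) ≤ 0.05; for example, P(X≤20 | 28, 0.85)=0.049. The other limits printed for n=15 to 65 match step 1. For Large ESFT at n=12, below 35% means 4 or fewer, and P(X≤4 | 12, 0.55)=0.112.

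**The case against.** The best defense has four parts.

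- **The final limit is not the only rule.** This is true. Sequential minimums and per-event reviews exist and catch some losses, as step 4 shows. But they stop or halt accrual when control is too low; none is a criterion for concluding that control is maintained.
- **A reader might infer that a clear loss usually passes.** The documents do not support that in general. At current sizes a 15-point loss passes the final limit less than half the time for RMS, STS and small/resected ESFT, and rarely at n=65. It passes more often than not at the first-phase Appendix D sizes for RMS, STS and small/resected ESFT, before the looks, and for Large ESFT at n=24. Appendix D is tied to Amendment 2.0, and 12.1 says the first 110 patients were complete in September 2007.
- **A reader might infer that the plan will report a passing group as having maintained efficacy.** No passage says so. It says only that falling below the limit is unacceptable. Objective 1.1 and section 12.1 are framed as estimation, and competing-risk estimates are planned. This softens the point but leaves 1.1.2, which says demonstrate, without any criterion.
- **The one-patient discrepancies are small**, and the 5% label is attached only to the second-phase limits, so applying it to the first-phase ones is an inference. A 35% cut-off at n=12 also still separates 4 from 5 patients although it is not an attainable rate. This is fair, and step 5 is a minor note.

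**Conclusion.** The objective and the decision rule do not match. Nothing in 12.1 or Appendix D can establish no reduction, and for the 85% target the bar falls as the group shrinks. A true 10-point loss passes the final limit with probability 60% to 83% at the current projected group sizes, and 33% to 42% at n=65. The sequential looks reduce these figures by an amount that depends on which reading of the stopping rule applies.

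The figures assume independent patients, each classified as controlled or not, with no censoring or competing deaths. The two pooled ESFT limits are computed here on the step 1 convention because none is printed. Losses of 10 and 15 points are illustrative, since the plan names no margin. Because the targets are not historical rates, even a rule that excludes loss would support a statement about the target only, not directly about earlier techniques.

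**What to change.** In 12.1 and Appendix D, report local control for each group with its 95% interval. Then choose one of two routes:

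- reword 1.1.2 as estimation against the target rates; or
- pre-state one threshold per target rate that does not change with n, claim 1.1.2 only if the one-sided 95% lower bound exceeds it, and otherwise report not demonstrated. Word the claim as relative to the target.

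The Appendix D limits should not serve as these thresholds. They depend on n and give 71.4% and 66.7% for two groups with the same 85% target.

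Also recompute every printed limit on one stated convention, add limits for the pooled ESFT sizes, and reconcile the text and footnote versions of the sequential rule.

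No patients or procedures are added. The cost is a claim that is harder to make. Purely as illustration, with the Appendix D limits as thresholds and the target true, the lower-bound rule is met 38% (n=28), 56% (n=24) and 48% (n=18) of the time. With phases pooled it is met 77% (RMS, 28+35=63), 87% (STS, 24+35=59) and 68% (small/resected ESFT, n=31). If the margin were 10, 15 or 20 points (an assumption), 80% power at the target would need 103, 49 or 31 patients (85% target), 82, 45 or 28 (90%), and 154, 71 or 41 (55%). With a strict margin, estimation is the more realistic route for most groups.

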2.0 Background

We will use the terminology musculoskeletal tumors (MST) to describe bone and soft tissue tumors that will be eligible for this protocol. MST includes Ewing's sarcoma family of tumors (ESFT), rhabdomyosarcoma (RMS), small round blue cell tumors that can only be classified as undifferentiated sarcoma, the soft-tissue tumors whose histiotypes are more commonly found in adults and classified as non-rhabdomyosarcoma soft-tissue sarcoma or soft-tissue sarcoma (STS), osteosarcoma (OS) and other localized tumors of the musculoskeletal tissues requiring focal therapy.

2.1 Issues in the Radiotherapeutic Management of Pediatric Sarcomas

The delivery of radiotherapy to pediatric patients with sarcomas is complicated, as one must balance the appropriate dose and volume of treatment needed for local control with radiotherapy's potential effects on developing tissues. These goals are often at odds with one another as critical structures are closely related geometrically to targets, and radiation tolerances of structures are not fully defined; as radiation techniques advance toward greater conformity of the high dose region to the target, lower heterogeneous doses are distributed more broadly in adjacent tissues (1,2).

The local control rates for Ewing's family sarcoma, rhabdomyosarcoma, and nonrhabdomyosarcoma soft tissue sarcoma are defined using conventional radiation therapy techniques prior to the conformal radiation therapy era (3-10). These techniques often deliver relatively high radiation doses to normal tissue not considered at risk for harboring microscopic or gross tumor. Image guided techniques may allow sparing of these normal tissues. Brachytherapy has also been utilized as a form of adjuvant radiotherapy in these tumor types, most commonly for non-rhabdomyosarcoma soft tissue sarcoma (11). Retrospective reviews of brachytherapy in pediatric patients appear to result in favorable local control rates but prospective data to confirm the benefit of this modality is needed (12). The addition of imaging with CT scans to assist in targeting and planning of brachytherapy cases should enhance the delivery of this local modality. We will test the hypothesis that treatment of pediatric sarcomas with image guided radiotherapy techniques will maintain at least the current levels of local tumor control achieved with conventional techniques, while studying the impact of 3dimensional, image-guided radiation techniques to potentially decrease radiationrelated normal tissue effects.

Patients treated on the RT-SARC protocol currently have local disease control outcomes at 2 years of 89% for patients with rhabdomyosarcoma (13), 94% for patients with soft-tissue sarcomas (14) and 95% for patients with Ewing's family tumors (unpublished data). These data begin to form the basis for local outcome measures with a well defined clinical cohort of patients receiving standardized, focal, limited-volume radiation therapy. Additional patient numbers and follow-up will help this cohort become the benchmark for future prospective focal radiation therapy studies measuring local disease control. Long term local control estimates obtained with 10+ year follow-up (or follow-up into adulthood 18 years of age}) will establish this as a reference dataset for future trials and comparisons.

Treatment related effects secondary to radiation therapy, both during and following treatment, have been a major area of concern relative to the use of therapeutic radiation in children and adolescents. The period of growth during the childhood and adolescent years is primarily responsible for the specific group of radiation related effects seen in children. These effects have often been ascribed to radiation by relating the site of the effect relative to the site of radiation treatment. Most historic information on treatment related effects of radiation is empiric and based on little data. Even in the adult radiation oncology community (where patient numbers are much greater than in pediatrics) definite normal tissue tolerances to radiation are not known (15). Data regarding treatment related effects of radiation on the pediatric patient are very limited and only correlate prescription doses of radiation with basic measurable endpoints (e.g. sitting and standing height or comparisons with normal populations) (16-20)). Prospective data in the pediatric population is noticeably absent. In the era of image guided radiation therapy, true analysis of the effects of radiation at a specific dose delivered to a specific volume may now be conducted. A prospective study in localized pediatric brain tumors conducted at St. Jude (RT-1) has made significant contributions to the understanding of these radiation dose and volume related effects (21,22). Within this study we propose to establish the needed baseline data to relate image guided radiotherapeutic parameters to functional and imaging measures of tissue function. This body of data will then allow meaningful comparisons with new treatment techniques and modalities.

Preliminary analyses from this clinical trial have yielded measures of normal tissue function (either structural, biochemical or functional) that appear to be well correlated with treatment dosimetry and clinical variables (23). As this dataset matures, additional patient cases accrued and more specific imaging implemented we anticipate to further refining the relationship of individual dosimetric features to quantifiable outcomes for normal tissue response. The additional numbers of cases and further specificity of imaging will add strength to our ability to correlate these outcomes.

Late effects of radiation continue to accumulate over time. Long term risks to bone integrity and strength result in fracture, altered bone growth or shape. Changes in soft tissue and organ function also continue to occur and evolve. Their cumulative effect on quality of life is frequently described relative to radiation therapy yet quality estimates do not exist in the context of well-defined dosimetry. Amendment 4.0 will focus on extending the long term follow-up of these patients as the protocol nears complete accrual. We will collect 5+ additional years of follow-up on the long-term survivors of this trial out to adulthood to better define and describe these effects. Imaging requirements will be reduced across the trial to transition this study towards a focus on long-term effect of therapy.

